Trial Sites:	
Clinical Coordinating Center
 
 • University of Pittsburgh, University of Pittsburgh Medical Center, PI [name], Co-PI [name] 
Additional Sites:
 
 • University of Alabama at Birmingham • University of Washington/ Harborview Medical Center • University of Tennessee Medical Center Knoxville • University of Texas Houston • University of Louisville • Vanderbilt University • University of Mississippi • University of Cincinnati • MetroHealth
Funding Agency	Department of Defense
IND Sponsor:	[name], MPH
Study Aims:	
AIM#1: Determine whether prehospital low titer whole blood as compared to standard prehospital resuscitation results in lower 30-day mortality in patients at risk of hemorrhagic shock.
 
AIM#2: Determine whether prehospital whole blood ($age > 14$ days) as compared to young whole blood ($age \leq 14$ days) is associated with equivalent clinical outcomes, hemostasis, prevention of coagulopathy, and platelet function in patients at risk of hemorrhagic shock.
 
AIM#3: Determine whether prehospital low titer whole blood as compared to standard prehospital resuscitation results in lower early mortality, blood and blood component transfusion requirements, incidence of coagulopathy, improved hemostasis and platelet function in patients at risk of hemorrhagic shock.

Study Design:	Open label, multi-center, pre-hospital randomized trial utilizing 10 level-1 trauma centers designed to determine the efficacy and safety of low titer whole blood resuscitation as compared to standard of care

	resuscitation in patients at risk of hemorrhagic shock and to appropriately characterize the hemostatic competency of whole blood relative to its age.
Planned Sample Size:	1020 patients
Planned Study Time:	6-year, multi-center study; 4-year enrollment
Major Inclusion Criteria:	
1.) Injured patients at risk of hemorrhagic shock being transported from scene or referral hospital to a participating TOWAR trial site that meet requirements for initiation of blood or blood component transfusion
 
AND
 
2A.) Systolic blood pressure ≤ 90mmHg and tachycardia (HR ≥ 108) at scene, at outside hospital or during transport
 
OR
 
2B.) Systolic blood pressure ≤ 70mmHg at scene, at outside hospital or during transport

Major Exclusion Criteria:	
 1. Wearing “NO TOWAR” opt-out bracelet 2. Age > 90 or < 18 years of age 3. Isolated fall from standing injury mechanism 4. Known prisoner or known pregnancy 5. Traumatic arrest with > 5 consecutive minutes of CPR without return of vital signs 6. Brain matter exposed or penetrating brain injury (GSW) 7. Isolated drowning or hanging victims 8. Objection to study voiced by subject or family member at the scene 9. Inability to obtain IV or intraosseous access 10. Isolated burns without evidence of traumatic injury
Primary Endpoint:	30-day mortality

I. Specific Aims

Resuscitation strategies for the acutely injured patient in hemorrhagic shock have evolved. Patients benefit from receiving less crystalloid and early red blood cell transfusion with balanced ratios of plasma and platelets.¹⁻³ These resuscitation practices are termed Damage Control Resuscitation and are incorporated into massive transfusion protocols in level 1 trauma centers across the country.²⁻⁴ This reconstituted strategy has also been coined ‘whole blood-like’ resuscitation despite being inferior compositionally to whole blood.^{5,6}

Despite these changes, deaths from traumatic hemorrhage continue to occur in the first hours following trauma center arrival, underscoring the importance of early interventions which provide benefit.^{1-3,7} Due to the time sensitive nature of the treatment of hemorrhage, the ideal resuscitation intervention would entail use of blood products containing all essential hemostatic

components, administration closest to time of injury, and mitigation of the devastating downstream consequences of shock and coagulopathy.

Whole blood transfusion following traumatic injury represents the ‘essential next step’ for the management of hemorrhagic shock post-injury. Prehospital whole blood is significant in that it brings this lifesaving hospital intervention to those patients who need it most, at a time before hemorrhagic shock and coagulopathy begin to have their detrimental consequences. We hypothesize that the initiation of whole blood resuscitation in the prehospital setting will significantly reduce the morbidity and mortality attributable to hemorrhagic shock post-injury as compared to standard prehospital resuscitation practice. Thus, a large pragmatic clinical trial is needed to definitively establish the efficacy and safety of whole blood resuscitation initiated in the prehospital setting. Only a high-quality clinical trial will provide the evidence to justify the use of this limited resource early post-injury.

Whole blood is a precious resource. The shelf life of the whole blood product depends on separation procedures and ranges from 21 to 35 days. The storage of whole blood leads to platelet dysfunction, cell lysis, and release of potassium and free heme which may reduce the resuscitative capacity of whole blood or contribute to end organ injury. The safety and efficacy of whole blood as a resuscitation fluid as it approaches its shelf life remains poorly characterized. The aims of the current Type O Whole blood and assessment of Age during prehospital Resuscitation (TOWAR) trial are to determine the efficacy and safety of whole blood resuscitation as compared to standard care resuscitation in patients at risk of hemorrhagic shock and to appropriately characterize the hemostatic competency of whole blood relative to its age.

AIM#1: Determine whether prehospital low titer whole blood as compared to standard prehospital resuscitation results in lower 30-day mortality in patients at risk of hemorrhagic shock.

AIM#2: Determine whether old prehospital whole blood (age > 14 days) as compared to young prehospital whole blood (age ≤ 14 days) is associated with equivalent clinical outcomes, hemostasis, prevention of coagulopathy, and platelet function in patients at risk of hemorrhagic shock.

AIM#3: Determine whether prehospital low titer whole blood as compared to standard prehospital resuscitation results in lower early mortality endpoints, blood and blood component transfusion requirements, lower incidence of coagulopathy, and improved hemostatic and platelet function in patients at risk of hemorrhagic shock.

II. Background and Significance

Initiation of the tenets of damage control resuscitation early, in the prehospital setting, has the potential to reduce downstream complications attributable to hemorrhage by intervening closer to the time of injury, prior to the development of coagulopathy, irreversible shock, and the ensuing inflammatory response.⁸⁻¹¹ Thawed plasma transfusion has been shown to safely reduce 30-day mortality when infused early, in the prehospital setting, in patients at risk of hemorrhagic shock and this separation of survival occurs within the first 3 hours.¹² (Figure 1.)

A recent secondary analysis from the PAMPer trial demonstrated that patients who received both plasma and red cells (an independent predictor of mortality in the cohort) in the prehospital setting, had the best adjusted survival. Patients receiving crystalloid resuscitation only, had the highest mortality.¹³ (Figure 2.)

We hypothesize that the initiation of low titer whole blood (LTWB O) resuscitation in the prehospital setting is the most effective resuscitation for those at risk of hemorrhage and significantly reduces the morbidity and mortality attributable to hemorrhagic shock post-injury as compared to standard prehospital resuscitation practice. A large pragmatic clinical trial is needed to definitively establish the efficacy and safety of whole blood resuscitation initiated in the prehospital setting and to characterize its effectiveness as a function of storage time. Only a high-quality clinical trial will provide the evidence to justify the use of this precious blood banking resource early post-injury.

Study Design/Setting: The current proposed trial will be a 6-year (4-year enrollment), multi-center, open label, prehospital randomized trial utilizing 10 level-1 trauma centers from within the LITES network and will enroll approximately 1020 patients. The University of Pittsburgh will be the Clinical Coordinating Center and the Data Coordinating Center for the study.

Study Population: Injured patients at risk of hemorrhagic shock requiring blood transfusion in prehospital phase of care.

Inclusion Criteria:

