For the primary trial outcome, an indicator of death within 30 days will be generated for each participant. A two-sided z-test for proportions controlling for within cluster correlation utilizing the methods of Donner and Klar will serve as the primary approach to compare the proportions between the treatment arms.²⁴ A mixed-effects logistics regression model will be used to assess the independent impact of LTWB on 30-day survival after controlling for potential confounding effects of baseline characteristics which reveal imbalance between treatment groups. Random effects will be included for intercept, slope, service. Fixed effects will include treatment, baseline characteristics not balanced through random assignment, and month of study.

Analyses to test for the homogeneity of the treatment effect will be carried out for the pre-defined subgroups. Regression models appropriate for the outcome variable (e.g., mixed effect logistic regression for binary outcome variables) will be used to test for the homogeneity of the treatment effect. Main effects will be included in the model for treatment, the indicator of the subgroup and the two-way interaction between treatment and subgroup. If a statistically significant interaction is observed, we will reject the null hypothesis of a homogenous treatment effect.

AIM#2 Analysis: Determine whether prehospital old whole blood (age > 14 days) as compared to young whole blood (age ≤ 14 days) is associated with similar clinical outcomes, hemostasis, prevention of coagulopathy, and platelet function in patients at risk of hemorrhagic shock.

The analysis will begin by describing the baseline demographic and clinical characteristics of the overall population and then stratified by age of whole blood; whole blood age ≤ 14 days versus whole blood age > 14 days. For discrete variables, proportions will be generated, and a chi-square test will be used to test for differences between the proportions. For continuous characteristics, means (medians) and standard deviations (interquartile ranges) will be calculated and t-tests (Wilcoxon) will be used to compare the means (distributions) between treatment arms.

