An unadjusted analysis comparing the 30-day mortality rate by blood age will be conducted using a chi-square test. Additionally, because of the observational nature of the study, a propensity adjusted analysis will be carried out to control for potential confounders (including biological sex, TBI, etc.). A generalized boosted regression model (GBM) will be used to generate a propensity score for each participant indicating the probability of receiving young whole blood. The GBM approach will be used to identify important characteristics that will be used to estimate the propensity scores. From this approach, a propensity score, $p(x)$, indicating the probability of receiving young whole blood given the observed characteristics will be obtained for each subject.

We will use the Toolkit for Weighting and Analysis of Nonequivalent Groups (twang) software package and the SAS/Stata macros (<http://www.rand.org/statistics/twang/downloads.html>) to estimate and evaluate the propensity scores. We will estimate the propensity score for each

subject by running the macro or command *ps* (dichotomous) or *mnp* (multinomial). That is, GBM will fit separate GBMs to each dummy treatment indicator to estimate the propensity score for the given phenotype. We will consider all the subject characteristics when fitting GBM. The GBM approach will select which characteristics to include and the best functional form including interactions. If missing data is present for the subject characteristics, twang will attempt to construct weights that also balance rates of missingness by creating indicator variables.

The maximum number of iterations for the GBM approach will be set to the default (i.e. 10000). The optimal number of iterations will be selected as the one that minimizes the balance statistics of interest. We will use the balance statistics *es.mean* and *ks.mean*. The *es.mean* uses the absolute standardized bias (also referred as the effect size or absolute standardized mean difference) and summarizes across variables, and the *ks.mean* uses the KS statistic to assess balances and summarizes across variables. We will allow a maximum of three splits for each tree in the model, allowing for three-way interactions between all covariates to be considered. The shrinkage parameter will be set to 0.0005 to ensure a smooth fit. The tuning parameters involved in the GBM models will be adjusted if necessary, until covariate balance is achieved.

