To evaluate the model, we will plot the balance statistics as a function of the number of iterations (higher iterations correspond to more complicated fitted models). If more iterations are needed, we will increase the number of iterations. Balance tables and plots will be generated to assess balance. Multiple pairwise sets of balance metrics will be evaluated. We will use the ES and the KS as balance metrics to assess whether the groups are balanced with respect to the observed baseline and pre-treatment characteristics. For the ES metric, a value under 0.20 is indicative of good balance. For the KS metric, a value under 0.10 will be indicative of good balance, but p-values will also be evaluated. The GBM fit (*es.mean* or *ks.mean*) that provides the best balance and yields the largest effective sample size will be preferred (McCaffrey et al., 2013). We will also plot the propensity score values using boxplots to compare the distributions and to evaluate the common support. Ideally, the propensity score distributions will overlap entirely; however, if there are areas of substantial non-overlap, we will discard subjects in those areas to increase generalizability. We will use a 1-dimensional function of the propensity score, referred to as the sensitivity function (SF), to quantify the hidden bias due to unmeasured confounders.

Variables in the GBM will include demographic characteristics, clinical characteristics, and site. A mixed-effects log-binomial regression model will then be used to estimate the independent effect of receiving young whole blood on 30-day mortality. The mixed effects log-binomial regression model will include an indicator of 30-day mortality as the dependent variable and indicator of the age of whole blood as the independent variable, with the propensity scores used as an inverse probability weight.

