Sample Size Justification and Power Analysis: The sample size calculations are based on the primary outcome, 30-day mortality, for Aim 1 of the study. With 40 service providers, a sample of 340 participants per treatment group is needed to detect a difference in the 30-day mortality rate of 26% vs. 16% (based on data from the PAMPer study), assuming 80% power, a type I error rate of 0.05, a two-sided alternative hypothesis, and an intraclass correlation coefficient of 0.02, as was observed in the PAMPer study.¹² The size of the ICC will have an impact on the size of the sample needed. If the ICC is smaller (e.g., 0.01 would require a sample size of 300 per arm), fewer people will be needed. However, if it is larger, more will be needed (e.g., 0.05 would require a sample size of 680 per arm).

Using a 2:1 random allocation of study participants to LTWB:standard of care, and enduring that there are 340 participants in the standard care arm, will lead to a total sample size of 1020, with 680 participants receiving LTWB. Assuming that 60% of these participants will receive whole blood \leq 14 days in age and 40% will receive whole blood $>$ 14 days in age, based on a chi-square test of proportions there will be 80% power to detect a higher mortality rate of 22.6% among those receiving whole blood over 14 days old, assuming a 30-day mortality rate of 14% among those receiving whole blood \leq 14 days, a type 1 error of 0.05 and a two-sided alternative hypothesis (that whole blood $>$ 14 days in age has a worse outcome than whole blood \leq 14 days) vs. the null hypothesis that whole blood $>$ 14 days is the same or better than whole blood \leq 14 days).

Randomization of Ineligible Subjects: It is anticipated that there will be a small proportion of patients enrolled who receive whole blood or standard care that in retrospect will not have met the entry criteria and are thus ineligible. In this circumstance, patients will be analyzed according to the group to which they were randomized. Subgroup analyses based on eligibility criteria will be performed if the number of patients so affected is large. However, based on the relatively

limited inclusion and exclusion criteria it is anticipated that the frequency of this event will be low.

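### Aim 2 asks whether old and young whole blood are equivalent, but the plan has only difference tests and effect estimates, with no margin or interval rule for equivalence

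*Combined protocol and SAP*

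**What the plan says.** The synopsis (Study Aims) and Section I (Specific Aims) both put Aim 2 as a question to be determined: whether old blood, compared with young blood, "is associated with equivalent clinical outcomes, hemostasis, prevention of coagulopathy, and platelet function in patients at risk of hemorrhagic shock". Section VI (AIM#2 Analysis) changes the adjective: "is associated with similar clinical outcomes, hemostasis, prevention of coagulopathy, and platelet function". Neither word is defined.

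The analysis in Section VI has three parts:

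- Unadjusted: "An unadjusted analysis comparing the 30-day mortality rate by blood age will be conducted using a chi-square test".
- Adjusted: "because of the observational nature of the study, a propensity adjusted analysis will be carried out to control for potential confounders". This leads to inverse-probability weighting and a model: "A mixed-effects log-binomial regression model will then be used to estimate the independent effect of receiving young whole blood on 30-day mortality".
- Other outcomes: mixed linear models, log-rank tests and Cox frailty models, chosen by outcome type.

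The Sample Size Justification and Power Analysis paragraph says that "there will be 80% power to detect a higher mortality rate of 22.6% among those receiving whole blood over 14 days old", taking 14% mortality with young blood and a 60/40 split of 680 recipients. The error rate and hypotheses are introduced as "a type 1 error of 0.05 and a two-sided alternative hypothesis (that whole blood", and the parenthesis goes on to give a directional pair: old blood does worse, against a null that it does as well or better.

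The only numerical thresholds in the Aim 2 analysis (0.20 for the effect-size metric, 0.10 for the KS metric) judge covariate balance. They are not outcome margins.

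**The concern.** The question and the method do not match. To conclude that two groups are equivalent, one states in advance how large a difference would still be acceptable and then shows that the confidence interval excludes anything larger. The plan does neither.

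In the power paragraph, old blood being no worse is the null hypothesis. The planned test can then favour the aim only by failing to reject, and failing to reject may simply reflect too few deaths. The propensity-weighted estimate would be more informative, but no criterion is given for reading it. As written, no result could answer the Aim 2 question with a justified yes.

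Section III names blood age as the principal secondary outcome, and Section I says that the safety and efficacy of whole blood near the end of its shelf life are poorly known. A finding of equivalence resting on a non-significant p value would bear directly on that safety question.

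**Working it through.** **Inputs** (Sample Size Justification and Power Analysis): 680 LTWB recipients; 60% young, 0.6 × 680 = 408; 40% old, 0.4 × 680 = 272; mortality 14% (young) and 22.6% (old); alpha 0.05. The sum 1/408 + 1/272 = 0.006127 recurs below.

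**Step 1. The plan's own figure.** Standard error under the alternative: sqrt(0.14×0.86/408 + 0.226×0.774/272) = 0.0306.

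- Unpooled, two-sided: 0.086/0.0306 - 1.960 = 0.85, power 80.2%.
- Pooled, two-sided: the mean rate is (0.14×408 + 0.226×272)/680 = 0.1744 and the null standard error is 0.0297, so (0.086 - 1.960×0.0297)/0.0306 = 0.91, power 81.8%.
- One-sided at 0.05: 87.8% (unpooled) to 88.7% (pooled).

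The stated 80% therefore reproduces as a two-sided test for a difference. It stands on the plan's own terms: a plain chi-square test with no clustering or weighting.

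**Step 2. What non-significant results would look like.** Old minus young, Wald 95% interval, chi-square without continuity correction:

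| Deaths, young | Deaths, old | Rates | p | 95% CI (points) |
|---|---|---|---|---|
| 57/408 | 38/272 | 14.0% vs 14.0% | 1.00 | -5.3 to +5.3 |
| 57/408 | 45/272 | 14.0% vs 16.5% | 0.36 | -3.0 to +8.1 |
| 57/408 | 53/272 | 14.0% vs 19.5% | 0.056 | -0.3 to +11.3 |

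The last row is deliberately an edge case: one more old-blood death (54/272) gives p = 0.042. Its upper limit exceeds the 22.6 - 14 = 8.6 points that the plan is powered to detect.

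**Step 3. How often a real excess would be missed.** At true rates of 14% and 19%, the mean rate is 0.16, the null standard error 0.0287 and the alternative standard error 0.0293. Power is Φ((0.05 - 1.960×0.0287)/0.0293) = Φ(-0.21) = 0.416, so the test is non-significant 58.4% of the time (58.3% by exact enumeration). For true excesses of 3 and 7 points the figures are 81% and 34%.

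**Step 4. What a margin-based claim could support at this size.** The documents give no margin, so these figures show what the sample size can resolve; they are not proposals. Assume equal true mortality of 14% (the plan's young-blood rate) or 16% (the lower rate in the Aim 1 calculation, read as the LTWB arm), and 80% power.

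- Risk difference: SE = sqrt(p(1-p)×0.006127) = 0.0272 / 0.0287.
  - Non-inferiority, 95% CI: (1.960 + 0.842)×SE = 7.6 / 8.0 points.
  - Equivalence, 90% CI: (1.645 + 1.282)×SE = 7.9 / 8.4 points.
- Risk ratio (a separate calculation, not a translation of the above): SE(log RR) = sqrt((1-p)/p × 0.006127) = 0.194 / 0.179.
  - Non-inferiority: exp(2.802×SE) = 1.72 / 1.65.
  - Equivalence: exp(2.927×SE) = 1.76 / 1.69.

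For scale, an equivalence margin of 5 points at 14% mortality (90% CI) would need 0.1204 × 2.927² / 0.05² × (1/0.6 + 1/0.4), or about 1,719 LTWB recipients, against 680 planned.

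Steps 2 to 4 include no loss from weighting, clustering or missing outcomes.

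**The case against.** The best defence is that this is one loose word in an aim whose working content is about association. The study design statement and Section I speak of characterizing whole blood by its age, Section III defines the principal secondary outcome as an association and adds five weekly age bins, and the weighted model is there to estimate an effect. Nowhere does the plan say that a non-significant result will be reported as equivalence. It is also fair that the examples describe the unadjusted comparison and not the weighted model, that 19% is an assumed rate, and that the third example sits at the significance edge.

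Much of this stands. The aim wording is what is out of line, and the models need no repair. But the word appears in both formal statements of the aims, under an instruction to determine whether it is true, and the softer word in the analysis section supplies no criterion either. The weighted analysis does not rescue the aim, since it has nothing to be judged against, and the mid-range example (p = 0.36) makes the point without the edge case.

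**Conclusion.** The concern holds. Aim 2 poses an equivalence question that the planned analysis cannot answer in the affirmative, because no margin or interval rule exists for any outcome. The size of the gap rests on the plan's 60/40 split and 14% young-blood mortality. Even identical observed rates leave about 5.3 points of uncertainty either way, and a true 5-point excess would be non-significant more often than not.

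This should be corrected, but it is limited to Aim 2: the Aim 1 comparison and its sample size are untouched, and the 22.6% power figure is sound as an unclustered, unweighted two-sided calculation. The directional hypotheses printed beside the two-sided label are a minor wording slip.

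**What to change.** **Recommended, wording only.**

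- In the synopsis, Section I and the AIM#2 Analysis heading, replace the aim with: *Estimate the association of prehospital whole-blood age (more than 14 days versus 14 days or less) with the outcomes listed for this aim.*
- Add to the AIM#2 Analysis: *Results will be reported as estimates with 95% confidence intervals; a non-significant result will not be reported as equivalence or similarity.*
- In the power paragraph, state the hypotheses as: *H0: 30-day mortality does not differ by whole-blood age; H1: it differs (two-sided).* The 22.6% figure stays.

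**Only if the sponsor wants to keep an equivalence or not-worse claim for 30-day mortality.** Before the data are seen, fix a clinically justified margin and a confidence level on one stated scale and direction. Apply them to the propensity-weighted estimate and write margin-based hypotheses for that claim. Say that the 22.6% power statement belongs to the separate difference test, and report the other Aim 2 outcomes as estimates.

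**Cost.** The recommended route changes no sample size, data collection or model. Its real price is that the sponsor gives up the stated equivalence question, which is a change of objective and the sponsor's decision. The alternative needs a margin that may be disputed, and the planned size may be too small for one that clinicians would accept.
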